**Table GBGF.7.2. Target Blood Glucose Values**

Insulin Therapy	Assess Blood Glucose Value	Target Blood Glucose	Adjust Insulin Dose
Basal Insulin	Pre-Morning Meal	$>70$ and $\leq 110$ mg/dL	Basal Insulin
Mixed Insulin	Pre-Morning Meal	$>70$ and $\leq 110$ mg/dL	Mixed Insulin (Pre-Evening Meal)
	Pre-Evening Meal	$>70$ and $\leq 110$ mg/dL	Mixed Insulin (Pre-Morning Meal)
Mealtime Insulin	Pre-Midday Meal	$>70$ and $\leq 110$ mg/dL	Mealtime Insulin (Pre-Morning Meal)
	Pre-Evening Meal	$>70$ and $\leq 110$ mg/dL	Mealtime Insulin (Pre-Midday Meal)
	Pre-Bedtime	$>70$ and $\leq 140$ mg/dL	Mealtime Insulin (Pre-Evening Meal)

### 7.2.1.3. Concomitant Oral Antidiabetic Medications

The use of 1 or 2 of the OADs (biguanides, TZD,  $\alpha$ -GI, and sodium-glucose co-transporter 2 inhibitors [SGLT2i]) is permitted during the study, provided the dose is stable for at least 3 months prior to Visit 1. These drugs must be used based on label information. Patients should remain on their prestudy OAD regimen for the screening and lead-in, and treatment periods. Patients who are taking concomitant OADs and who develop a condition that is a contraindication will be considered ineligible and must be discontinued from the study before randomization. No change in dosage or administration of OADs is allowed during the 16-week primary treatment period. During the 36-week extension treatment period, the investigator is to consult with the Lilly Clinical Research Physician (CRP) or Clinical Research Scientist (CRS) if the dosage or administration of OADs is changed.

## 7.3. Blinding

This study includes a 16-week double-blind (dulaglutide versus placebo) primary treatment period, and a 36-week open-label extension treatment period.

To preserve the blinding of the study, the treatment assignments in the double-blind period will be blinded to patients and investigators until study completion.

Emergency unblinding for AEs may be performed through the IWRS, which may supplement or take the place of emergency codes generated by a computer drug-labeling system. This option may be used ONLY if the patient's well-being requires knowledge of the patient's treatment assignment. All actions resulting in an unblinding event are recorded and reported by the IWRS.

If an investigator, site personnel performing assessments, or patient is unblinded, the patient must be discontinued from the study. In cases where there are ethical reasons to have the patient remain in the study, the investigator must obtain specific approval from a Lilly CRP or CRS for the patient to continue in the study.

In case of an emergency, the investigator has the sole responsibility for determining if unblinding of a patient's treatment assignment is warranted. Patient safety must always be the first consideration in making such a determination. If the investigator decides that unblinding is warranted, the investigator should make every effort to contact the Lilly CRP or CRS prior to unblinding a patient's treatment assignment unless this could delay emergency treatment of the patient. If a patient's treatment assignment is unblinded, Lilly must be notified immediately.

## **7.4. Dosage Modification**

The dosage of investigational product (dulaglutide or placebo) cannot be adjusted (see Section 7.2.1.1).

During the 16-week primary treatment period, the patient's insulin dose is to remain fixed. The insulin dose may be adjusted to maintain target glucose values during the 36-week extension treatment period (Section 7.2.1.2). For patients treated with 1 or 2 OADs prior to Visit 1, no change is allowed during the 16-week primary treatment period; during the 36-week extension treatment period, the investigator is to consult with the Lilly CRP or CRS if the dosage or administration of OADs is changed (7.2.1.3).

### **7.4.1. Special Treatment Considerations**

#### **7.4.1.1. Standards of Medical Care**

Maintenance of adequate glycemic control in study participants may be enhanced but should not be compromised due to trial participation. Investigators and other study team members are expected to treat patients according to the nationally established standard of care for diabetes management (Japan Diabetes Society, 2013), except where that treatment would be in conflict with the protocol-provided treatment requirements.

This section provides guidance on management of hypoglycemic events and episodes of severe, persistent hyperglycemia. For effective implementation of measures described here, it is important that patients, and their caregivers, if applicable, be well-educated about the signs and symptoms of hypoglycemia (for example, intense hunger, sweating, tremor, restlessness, irritability, depression, headaches, disturbed sleep, or transient neurological disorders) and hyperglycemia (for example, severe thirst, dry mouth, frequent micturition, or dry skin). Patients should be instructed to contact the investigative site in the event of severe hypoglycemia or severe, persistent hyperglycemia (Section 7.4.1.3) between study visits.

#### **7.4.1.2. Management of Increased Hypoglycemia Risk**

If a hypoglycemic event occurs, the patient should record in the study diary the plasma glucose (PG) level measured during the episode and, prior to administration of treatment (if taken), associated symptoms, and treatment administered. Site personnel should educate and encourage

patients to measure and record PG values during the symptoms of hypoglycemia in their study diaries. Patients should be instructed to call the investigative site as soon as possible if they experience a hypoglycemic event that requires assistance to administer treatment.

Investigators should use the following definitions and criteria when diagnosing and categorizing an episode considered to be related to hypoglycemia (the PG values in this section refer to values determined by a laboratory or International Federation of Clinical Chemistry and Laboratory Medicine plasma-equivalent glucose meters and strips) (ADA 2005):

- **Documented symptomatic hypoglycemia** is defined as any time a patient feels that he/she is experiencing symptoms and/or signs associated with hypoglycemia, and has a PG level of  $\leq 70$  mg/dL ( $\leq 3.9$  mmol/L).
- **Asymptomatic hypoglycemia** is defined as an event not accompanied by typical symptoms of hypoglycemia but with a measured PG of  $\leq 70$  mg/dL ( $\leq 3.9$  mmol/L).
- **Probable symptomatic hypoglycemia** is defined as an event during which symptoms of hypoglycemia are not accompanied by a PG determination (but that was presumably caused by a PG concentration of  $\leq 70$  mg/dL [ $\leq 3.9$  mmol/L]).
- **Severe hypoglycemia** is defined as an episode requiring the assistance of another person to actively administer carbohydrate, glucagon, or other resuscitative actions. These episodes may be associated with sufficient neuroglycopenia to induce seizure or coma. Plasma glucose measurements may not be available during such an event, but neurological recovery attributable to the restoration of PG to normal is considered sufficient evidence that the event was induced by a low PG concentration.
- **Nocturnal hypoglycemia** is defined as any hypoglycemic event that occurs between bedtime and waking.

Cases of relative hypoglycemia, defined as symptomatic events during which the person reports any of the typical symptoms of hypoglycemia and interprets those as indicative of hypoglycemia, but with a measured PG concentration of  $>70$  mg/dL ( $>3.9$  mmol/L), will also be collected.

If a hypoglycemic event meets the criteria of severe, it needs to be recorded as serious on the AE case report form (CRF) and reported to Lilly as an SAE.

#### 7.4.1.3. Management of Severe, Persistent Hyperglycemia

During the 16-week primary treatment period, if a patient experiences severe, persistent hyperglycemia, the patient must discontinue from study. Severe, persistent hyperglycemia is defined as follows; the patient's fasting SMPG concentrations are consistently above the fasting plasma glucose threshold (see below) for at least 2 weeks.

Week of Study Treatment	Weeks 0-4	Weeks 5-16
Average Fasting Plasma	$>15.0$ mmol/L	$>13.3$ mmol/L
Glucose for 2 weeks	$>270$ mg/dL	$>240$ mg/dL

### **7.5. Preparation/Handling/Storage/Accountability**

The study site must store the SDP cartons in a locked and secure environment. The SDPs must be refrigerated (not frozen) at 2°C to 8°C until use. Dry ice should not be used for cooling. Patients will be provided with cartons containing 4 dulaglutide or placebo SDPs, as required, at clinical visits per the Schedule of Activities (Section 2). They will receive insulated bags with cooling gel packs for use in transporting the SDP carton from the site to home. Investigational products will be labeled according to Japan's regulatory requirements.

Dulaglutide demonstration pens will be provided for subcutaneous injection training at the site; these pens do not have needles and do not contain investigational product.

Patients will also be provided with a commercially available PG meter and test strips to use during the study. Sufficient investigational product and glucose testing supplies will be dispensed, as needed, at each visit.

Study site staff must regularly assess whether the patient is correctly administering the assigned investigational product and storing the investigational product according to the provided instructions.

### **7.6. Treatment Compliance**

Patient compliance with study medication will be assessed at each visit by the investigator, based on the patient's adherence to the visit schedule and compliance with the study medication assessed by study diaries. Initially, patients considered as poorly compliant with their medication and/or the study procedures will receive additional training and instruction, as required, and be reminded of the importance of complying with the protocol.

Overall treatment compliance is defined as taking at least 75% of the required doses of investigational product. Compliance is further defined as not missing more than 2 consecutive weekly injections of dulaglutide or >14 consecutive daily injections of insulin. Similarly, a patient will be considered significantly noncompliant if he/she is judged by the investigator to have intentionally or repeatedly taken more than the prescribed amount of medication.

### **7.7. Concomitant Therapy**

Patients are permitted to use concomitant medications that they require during the study, except certain medications that may interfere with the assessment of efficacy and safety characteristics of the investigational product.

Investigative site staff will inform patients that they must consult with the investigator or a designated site staff member upon being prescribed any new medications during the study, except when initiated for treatment of medical emergencies. Any additional medication initiated during the course of the study (including over-the-counter [OTC] drugs, such as paracetamol or aspirin) must be documented, and the name of the drug, the dosage (OADs only), and the date(s) of administration must be recorded in the patient's diary and on the "Concomitant Medications" section of the eCRF.

Nonstudy medications taken by patients who are screened but not randomized will not be reported to Lilly unless the medication is associated with an SAE or AE that the investigator believes may have been caused by a study procedure.

If the following prohibited drugs are used by a patient, the patient must discontinue from the study.

### **7.7.1. Oral Antidiabetic Medications**

In the screening and lead-in period, DPP-4 inhibitors, SU, and glinides will be washed out, and are not permitted during the treatment period. Dulaglutide and DPP-4 inhibitors decrease blood glucose via the GLP-1 receptor; this combination has not been investigated for efficacy and safety in clinical studies. Sulfonylureas and glinides increase the risk of hypoglycemia in combination with dulaglutide (Emoto et al. 2015).

### **7.7.2. Nonstudy Glucagon-Like Peptide-1 Receptor Agonists**

Nonstudy GLP-1 receptor agonists (for example, liraglutide or exenatide) are not allowed at any time during the study.

### **7.7.3. Systemic Glucocorticoids**

Systemic glucocorticoid therapy for >14 consecutive days (with the exception of topical, intraocular, or intranasal preparations) within 4 weeks prior to Visit 1 is exclusionary, and is not allowed at any time during the study. Patients who require >14 days of therapy with these medications at any time during the treatment period must immediately be discontinued from the study.

### **7.7.4. Medications that Promote Weight Loss**

Medications that promote weight loss are not allowed at any time during the study.

## **7.8. Treatment after the End of the Study**

### **7.8.1. Continued Access**

Dulaglutide will not be made available after conclusion of the study to patients.

## 8. Discontinuation Criteria

### 8.1. Discontinuation from Study Treatment

Investigational product may be interrupted temporarily or discontinued permanently. Those patients who stop the investigational product permanently will also be immediately discontinued from the study.

#### 8.1.1. *Permanent Discontinuation from Study Treatment and Study*

Patients will be permanently discontinued from investigational product and from the study in the following circumstances:

- For inadvertently enrolled patients for whom it was determined that continued treatment with investigational product would not be medically appropriate (see Section 8.1.3);
- The patient misses more than 2 consecutive weekly injections of investigational product or more than 14 consecutive daily injections of insulin;
- The patient's fasting SMPG concentrations are consistently above the fasting plasma glucose threshold for at least 2 weeks (see Section 7.4.1.3)
- The patient becomes pregnant during the study, in which case, the patient must discontinue the study immediately and Lilly or its designee is to be informed immediately;
- The patient is diagnosed with acute pancreatitis or acute hepatitis;
- The patient develops Exclusion Criterion [23] (eGFR <30 mg/min/1.73m^2);
- The patient is diagnosed with C-cell hyperplasia or medullary thyroid carcinoma;
- The patient uses or needs to use additional antidiabetic medication or prohibited medication (for example, weight loss medication; see Section 7.7);
- The patient requires >14 days of therapy with systemic glucocorticoids;
- Enrollment in any other clinical trial involving an investigational product or enrollment in any other type of medical research judged not to be scientifically or medically compatible with this study;
- Sponsor decision
  - Sponsor stops the study or stops the patient's participation in the study for medical, safety, regulatory, or other reasons consistent with applicable laws, regulations, and good clinical practice (GCP)
- Investigator decision
  - The investigator decides that the patient should be discontinued from the study

- If the patient, for any reason, requires treatment with another therapeutic agent that has been demonstrated to be effective for treatment of the study indication, discontinuation from the study occurs prior to introduction of the new agent
- Patient decision
  - The patient requests to be withdrawn from the study

Discontinuation of the investigational product for abnormal liver tests **should be considered** by the investigator when a patient meets 1 of the following conditions after consultation with the Lilly CRP or CRS:

- ALT or aspartate aminotransferase (AST) >8X upper limit of normal (ULN)
- ALT or AST >5X ULN for more than 2 weeks
- ALT or AST >3X ULN and total bilirubin level (TBL) >2X ULN or prothrombin time >1.5X ULN
- ALT or AST >3X ULN with the appearance of fatigue, nausea, vomiting, right upper-quadrant pain or tenderness, fever, rash, and/or eosinophilia (>5%)
- alkaline phosphatase (ALP) >3X ULN
- ALP >2.5X ULN and TBL >2X ULN
- ALP >2.5 ULN with the appearance of fatigue, nausea, vomiting, right-quadrant pain or tenderness, fever, rash, and/or eosinophilia (>5%)

Patients who discontinue investigational product and the study early will complete the early termination (ET) visit and safety follow-up visit as shown in the Schedule of Activities (Section 2), unless the patient withdraws consent. At the ET visit, the investigator will prescribe an appropriate antihyperglycemia regimen and SMPG monitoring plan to be followed after completion of the study.

### **8.1.2. Temporary Interruption of Study Treatment**

In certain situations after randomization, the investigator may need to temporarily discontinue (interrupt) investigational product (for example, due to an AE or a clinically significant laboratory value). If investigational product discontinuation is due to an AE, the event is to be documented and followed according to the procedures in Section 9.2 of this protocol.

### **8.1.3. Discontinuation of Inadvertently Enrolled Patients**

If the sponsor or investigator identify a patient who did not meet enrollment criteria and was inadvertently enrolled, a discussion must occur between the sponsor CRP or CRS and the investigator to determine if the patient may continue in the study. If both agree it is medically appropriate to continue, the investigator must obtain documented approval from the sponsor CRP or CRS to allow the inadvertently enrolled patient to continue in the study with or without treatment with investigational product.

## **8.2. Discontinuation from the Study**

Patients who discontinue investigational product must discontinue from the study (see Section [8.1.1](#)).

## **8.3. Lost to Follow-Up**

A patient will be considered lost to follow-up if he or she repeatedly fails to return for scheduled visits and is unable to be contacted by the study site. Site personnel are expected to make diligent attempts to contact patients who fail to return for a scheduled visit or were otherwise unable to be followed up by the site.

## 9. Study Assessments and Procedures

Section 2 lists the Schedule of Activities, with the study procedures and their timing (including tolerance limits for timing).

Appendix 2 lists the laboratory tests that will be performed for this study.

Unless otherwise stated in the subsections below, all samples collected for specified laboratory tests will be destroyed within 60 days of receipt of confirmed test results. Certain samples may be retained for a longer period, if necessary, to comply with applicable laws, regulations, or laboratory certification standards.

### 9.1. Efficacy Assessments

#### 9.1.1. Primary Efficacy Assessments

The primary efficacy measure is change in HbA1c from baseline at 16 weeks.

#### 9.1.2. Secondary Efficacy Assessments

The following secondary efficacy measures will be evaluated at 16 and 52 weeks:

- Change from baseline in HbA1c (52 weeks)
- Percentage of patients achieving HbA1c targets of  $<7.0\%$  or  $\leq 6.5\%$ , as measured at the central laboratory
- Changes from baseline in FSG measured at the central laboratory
- Changes from baseline in PG from 7-point SMPG profiles
- Changes from baseline in body weight
- Changes from baseline in insulin dose

#### 9.1.3. Exploratory Health Outcome/Quality of Life Measures

The following health outcomes and dietary measures listed below will be assessed according to the Schedule of Activities (Section 2); these are considered exploratory objectives of the study. The questionnaires will be given to the patient by the investigator or site staff and self-completed by the patient during the visit. The investigator or site staff will be responsible for checking for missing responses before the patient leaves the site. The questionnaires should be completed before any other study procedures, if the patient is not adversely affected by the fasting condition, or completed after the patient has sufficiently recovered from the visit procedures.

- The Diabetes Therapy Related-Quality of Life (DTR-QOL) is a disease-specific, self-administered questionnaire to assess the influence of diabetes treatment on patient quality of life, regardless of treatment method. The DTR-QOL consists of “burden on social activities and daily activities” (13 items), “anxiety and dissatisfaction with treatment” (8 items), “hypoglycemia” (4 items), and “satisfaction with treatment” (4 items). Each

question is rated on a 7-point scale, with higher scores indicating higher quality of life (4 scores in “satisfaction with treatment” must be reversed).

- The Diabetes Treatment Satisfaction Questionnaire status (DTSQs) is a patient-reported assessment of treatment satisfaction (6 questions) and perceived frequency of severe hypoglycemia and hyperglycemia (2 questions). Each question is rated on a 7-point scale from 0 to 6, with higher scores indicating either greater treatment satisfaction or greater perceived frequency of hypoglycemic or hyperglycemic events.
- The Device Questionnaire is a self-administered questionnaire to assess the usability and preference of Ateos (the name of device for Trulicity in Japan) compared to the insulin device the patient has been using so far. The questionnaire consists of 2 sections. In the first section, patients will respond to 12 items about usability and preference using a 5-point scale (from “Strongly Agree” to “Agree” in insulin device, both devices are the same, and from “Strongly Agree” to “Agree” in Ateos). In the second section, patients are asked whether each procedure to prepare and inject was cumbersome or not for Ateos (3 procedures) and insulin device (6 items). The patients’ response is chosen from rarely, sometimes, or always cumbersome in each procedure. This questionnaire was developed by the study team based on the previous research (Bailey et al. 2011; Oyer et al. 2011).
- The Dietary Evaluation will explore the relationship between meal preference and efficacy of dulaglutide in Japanese patients with T2D. Patients are required to complete a meal record (picture and record sheet) on 2 days during the 2-week period immediately before: Visit 3 (Week 0), Visit 7 (Week 16), or Visit 12 (Week 52). The timing of the meal record should be on the same date as 7-point SMPG measurements (except for 52 weeks). The Lilly designated vendor will calculate the total fats, total carbohydrates, total protein, and caloric intake amount based on the meal record.

#### **9.1.4. Appropriateness of Assessments**

Efficacy and safety assessments included in this study are generally regarded as reliable and accurate with respect to the efficacy and safety assessments in individuals and populations with T2D.

## **9.2. Adverse Events**

Investigators are responsible for monitoring the safety of patients who have entered this study and for alerting Lilly or its designee to any event that seems unusual, even if this event may be considered an unanticipated benefit to the patient.

The investigator is responsible for the appropriate medical care of patients during the study.

Investigators must document their review of each laboratory safety report.

The investigator remains responsible for following, through an appropriate health care option, AEs that are serious or otherwise medically important, considered related to the investigational product or the study, or that caused the patient to discontinue the investigational product before completing the study. The patient should be followed until the event resolves, stabilizes with

appropriate diagnostic evaluation, or is reasonably explained. The frequency of follow-up evaluations of the AE is left to the discretion of the investigator.

Lack of drug effect is not an AE in clinical studies, because the purpose of the clinical study is to establish treatment effect.

After the informed consent form (ICF) is signed, study site personnel will record via eCRF the occurrence and nature of each patient's preexisting conditions, including clinically significant signs and symptoms of the disease under treatment in the study. In addition, site personnel will record any change in the condition(s) and any new conditions as AEs. Investigators should record their assessment of the potential relatedness of each AE to study procedure, investigational product, and study device via eCRF.

The investigator will interpret and document whether or not an AE has a reasonable possibility of being related to study treatment, study device, or a study procedure, taking into account the disease, concomitant treatment, or pathologies.

A "reasonable possibility" means that there is a cause and effect relationship between the investigational product, study device, and/or study procedure and the AE.

The investigator answers yes/no when making this assessment.

Planned surgeries and nonsurgical interventions should not be reported as AEs unless the underlying medical condition has worsened during the course of the study.

If a patient's investigational product is discontinued as a result of an AE, study site personnel must report this to Lilly or its designee via eCRF, clarifying if possible, the circumstances leading to any dosage modifications, or discontinuations of treatment.

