### **9.2.1. Serious Adverse Events**

An SAE is any AE from this study that results in 1 of the following outcomes:

- death
- initial or prolonged inpatient hospitalization
- a life-threatening experience (that is, immediate risk of dying)
- persistent or significant disability/incapacity
- congenital anomaly/birth defect
- considered significant by the investigator for any other reason: important medical events that may not result in death, be life-threatening, or require hospitalization may be considered serious, based upon appropriate medical judgment.

Although all AEs occurring after signing the ICF are recorded in the eCRF, SAE reporting begins after the patient has signed the ICF and has received investigational product. However, if an SAE occurs after signing the ICF, but prior to receiving investigational product, it needs to be reported ONLY if it is considered reasonably possibly related to study procedure.

Study site personnel must alert Lilly or its designee of any SAE within 24 hours of investigator awareness of the event via a sponsor-approved method. If alerts are issued via telephone, they are to be immediately followed with official notification on study-specific SAE forms. This 24-hour notification requirement refers to the initial SAE information and all follow-up SAE information.

Pregnancy (during maternal or paternal exposure to investigational product) does not meet the definition of an AE. However, to fulfill regulatory requirements any pregnancy should be reported following the SAE process to collect data on the outcome for both mother and fetus.

Investigators are not obligated to actively seek AEs or SAEs in patients once they have discontinued and/or completed the study (the patient summary CRF has been completed). However, if the investigator learns of any SAE, including a death, at any time after a patient has been discharged from the study, and he/she considers the event reasonably possibly related to the study treatment or study participation, the investigator must promptly notify Lilly.

Requirements for the reporting of severe hypoglycemia episodes, AEs of pancreatitis, and AEs of systemic hypersensitivity as SAEs are found in Section 9.2.2.

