#### **9.2.1.1. Suspected Unexpected Serious Adverse Reactions**

Suspected unexpected serious adverse reactions (SUSARs) are serious events that are not listed in the package insert and that the investigator identifies as related to investigational product or procedure. United States 21 CFR 312.32 and European Union Clinical Trial Directive 2001/20/EC and the associated detailed guidances or national regulatory requirements in participating countries require the reporting of SUSARs. Lilly has procedures that will be followed for the recording and expedited reporting of SUSARs that are consistent with global regulations and the associated detailed guidances.

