#### 5.14.1. Adverse Events

An adverse event is any untoward medical event associated with the use of a drug in humans, whether or not it is considered related to a drug. Adverse events will be classified according to the Medical Dictionary for Regulatory Activities (MedDRA) and summarized by treatment group. Adverse events will be summarized as treatment-emergent adverse events (TEAEs) defined as events that are newly reported or reported to worsen in severity after the initiation of study drug through the treatment period. The incidence of patients with at least one TEAE and the incidence of TEAEs by MedDRA preferred term and system organ class will be presented by treatment group. The incidence of patients with at least one TEAE that is considered to be possibly related to the study drug in the opinion of the investigator will also be summarized. Fisher's exact test will be used for treatment comparison.

SAEs and AEs leading to discontinuation of the study drug will also be summarized and listed.

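### Protocol 9.2 defines a reasonable possibility of relatedness as an existing cause and effect relationship, so plausible but unproven reactions could be answered no and under-counted as related

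*Protocol*

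**What the plan says.** Protocol 9.2 has three statements on causality that bear on this point, and a definition.

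- On what goes into the database: "Investigators should record their assessment of the potential relatedness of each AE to study procedure, investigational product, and study device via eCRF".
- On the question itself, the investigator is to interpret and document "whether or not an AE has a reasonable possibility of being related to study treatment, study device, or a study procedure".
- On the form of the answer: "The investigator answers yes/no when making this assessment".
- On the meaning of the key term, a reasonable possibility "means that there is a cause and effect relationship between the investigational product, study device, and/or study procedure and the AE".

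Other sections rely on this judgement in their own words. Protocol 9.2.1 makes the duty to notify the sponsor of an SAE learned of after discharge depend on whether "he/she considers the event reasonably possibly related to the study treatment or study participation", and uses similar possibility wording for SAEs before the first dose. Protocol 9.2.1.1 counts as SUSARs those unlisted serious events "that the investigator identifies as related to investigational product or procedure". SAP 5.14.1 provides, on a per-patient count, that a "TEAE that is considered to be possibly related to the study drug in the opinion of the investigator will also be summarized".

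**The concern.** The question is framed as a possibility, but the definition describes a fact. It contains no *may*, *suspected* or *possible*. With only yes and no available, an investigator who suspects the drug but cannot say that it caused the event has no middle category, and on the literal definition does not meet the condition for yes.

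Two things are at stake. The first is the meaning of the related-TEAE summary. If some sites follow the definition and others follow the ordinary sense of *possibility*, one yes/no field carries two thresholds. If all follow the definition, the table would leave out events that its title suggests it contains. The second is the set of reporting steps that depend on the same answer. Literal use can only move answers from yes to no, so any error lowers the count of related events. Long-term safety up to 56 weeks is a stated objective.

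**Working it through.** The plan gives no figure for related events, so there is nothing to reproduce. The check sets the wordings side by side, traces where the answer is used, and bounds the effect.

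**1. Strength of each wording**

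- Protocol 9.2, recording in the eCRF: *potential* relatedness. Possibility.
- Protocol 9.2, the question: a *reasonable possibility*. Possibility.
- Protocol 9.2, the definition: there *is* a cause and effect relationship. Established causation.
- Protocol 9.2.1, SAEs before first dose and after discharge: *reasonably possibly* related. Possibility.
- Protocol 9.2.1.1, SUSARs: identified as *related*. No qualifier, so it takes its meaning from 9.2.
- SAP 5.14.1: *possibly* related in the investigator's opinion. Possibility.

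The definition is the only statement that asks for established causation. It is also the only definition of the term in either document.

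**2. What depends on the answer**

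- The SAP 5.14.1 summary of possibly related TEAEs, and the relationship shown in the listings of Protocol 10.3.4.2.
- SUSAR identification, as Protocol 9.2.1.1 defines it.
- SAEs before the first dose (relation to study procedure only) and SAEs learned of after discharge, in Protocol 9.2.1.
- The additional data on allergic or hypersensitivity reactions in Protocol 9.2.2.5, collected only where the investigator deems the event related to investigational product. The reactions themselves are reported whatever the causality.

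**3. What does not depend on it**

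- TEAE incidence by preferred term and system organ class, and the SAE and discontinuation summaries (SAP 5.14.1).
- Notification of any SAE within 24 hours once the patient has received investigational product and is on study (Protocol 9.2.1).
- Adjudication of pancreatic events, deaths and nonfatal cardiovascular events (Protocol 9.2.2.2 and 9.2.2.4; SAP 5.14.6).
- Reporting of severe hypoglycemia as an SAE (Protocol 7.4.1.2).

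**4. Bound on the effect**

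Let N be the number of events judged plausible but unproven, and q the share of them answered no because of the definition. The number of related events lost is q × N. The documents give neither N nor q. With q assumed anywhere from 0 to 1, the loss runs from 0 × N = 0 to 1 × N = N, that is, from none to all.

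The SAP summary counts patients with at least one related TEAE, not events. A patient leaves that count only if every one of his or her related events is answered no, so the loss in patients can be proportionally smaller than the loss in events.

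For the blinded 16-week comparison, suppose the true proportions of patients are p1 and p0 and the same share s of those patients is lost in each arm. The observed difference is then p1(1 − s) − p0(1 − s) = (1 − s)(p1 − p0). The difference shrinks by the factor 1 − s and the ratio is unchanged. Equal loss in both arms is an assumption.

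**The case against.** The strongest reply is that nobody is told to answer no to a plausible reaction. The question, the recording instruction, Protocol 9.2.1 and SAP 5.14.1 all speak of possibility, and investigators may well be guided by them. There is also a milder reading of the definition. Protocol Appendix 1 defines an AE as any untoward occurrence temporally associated with the product, whether or not related. The sentence in 9.2 may only be saying that the relation in question is causal rather than temporal, with reasonable possibility still the threshold. This stands as a plausible intention, and it is why the point is conditional. It does not remove the defect, because the sentence as printed does not say that, and a site is entitled to follow an express definition.

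A reader might also infer that serious events which are only possibly related would not reach the sponsor. The documents do not support that. Any on-study SAE after first dose must be notified within 24 hours whatever its causality. Only the pre-dose and post-discharge reports in Protocol 9.2.1 depend on relatedness. For SUSARs, Protocol 9.2.1.1 refers to sponsor procedures that are not reproduced, so loss of SUSARs cannot be shown. What can be said is that identification as 9.2.1.1 words it rests on the investigator's answer.

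It is also fair to say that related TEAEs are not among the safety endpoints in Protocol Table GBGF.4.1, and that the SAP table is supplementary. An event answered yes under a stricter standard is still at least possibly related, so the risk is an incomplete table rather than false entries in it. These points limit the consequence.

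**Conclusion.** The point holds as an internal inconsistency with a possible downward effect. The definition in Protocol 9.2 is stricter than the term it defines and than the other possibility wording in both documents, and the forced yes/no answer leaves no room between the two standards. Plausible but unproven reactions could be answered no, and the possibly related TEAE summary and the other uses traced above could be affected to that extent.

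A reader might go further and conclude that such reactions will be answered no and will drop out, or might put a percentage on the shortfall. Neither follows. The first assumes that every investigator applies one sentence literally and ignores the wording around it. The second needs a rate of related events and a rate of literal application, and the documents give neither. The assumptions needed for any effect at all are that some investigators follow the definition as written, and that the eCRF instructions, which are not among the documents, do not override it. The broad safety assessment, which rests on all-causality and adjudicated data, stands either way.

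**What to change.** Reword the definition in Protocol 9.2, for example: *A reasonable possibility means that a causal link between the event and the investigational product, the device or a study procedure may exist; the link need not be established.* Use the same term in Protocol 9.2.1 and 9.2.1.1 and in SAP 5.14.1, and preferably also in Protocol 9.2.2.5. Check the eCRF completion instructions against it.

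The cost is one sentence and some alignment of terms. No design element and no efficacy analysis changes. Related-event counts may be somewhat higher, and so look less favourable. If the change is made after patients have been treated, answers before and after it may rest on different thresholds, so the date should be recorded and mentioned when the related-TEAE summary is reported.
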